18.3 Efficacy Study Stopping Rule

Should the treatment not achieve a reduction in RV:LV ratio as measured by CT at 48 hours by at least 0.06 compared to baseline, in three of the first three patients, the study shall be paused for re-evaluation.

18.4 Device Study Stopping Rules

- 18.4.1 Should it be suspected that a device caused a serious adverse event, the serious adverse event will be adjudicated by the independent DSM and the device shall be returned to the manufacturer. A root cause analysis shall be performed. The DSM will determine if the study should be stopped, temporarily suspended, or continued after each such event.
- 18.4.2 There are device malfunctions, or non-conformances, that may impact the patient and prevent treatment with an investigational device. Upon commencement of enrollment, if there are device failures that prevent three (3) patients from being treated in this study, the study shall be paused for re-evaluation. A root cause analysis will be performed to determine the cause(s) of the device failures and a corrective and preventative action will be implemented.

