1.0 PROTOCOL SYNOPSIS (CONTINUED)

POPULATION	Patients 18 years of age or older who present with symptoms of acute submassive PE within 14 days of onset of symptoms will be considered for this study.
STUDY DESIGN	Prospective, non-randomized, multi-center study.
STUDY OBJECTIVE	Assess the safety and feasibility of the Bashir™ Endovascular Catheter for the administration of low dose thrombolytic for acute submassive pulmonary embolism.
SAMPLE SIZE	Up to ten (10) subjects will be enrolled and treated.
SITES	Up to five (5) sites will be qualified to participate in this study.
PRIMARY ENDPOINTS	
1. Safety: Major bleeding, as defined by International Society of Thrombosis and Hemostasis (ISTH), within 72 hours of initiation of r-tPA administration. Bleeding criteria are as follows: Major Bleeding in Non-Surgical Patients
 
 a. Fatal bleeding; and/or b. Symptomatic bleeding in a critical area or organ, such as intracranial, intraspinal, intraocular, retroperitoneal, intraarticular or pericardial, or intramuscular with compartment syndrome; and/or c. Bleeding causing a fall in hemoglobin level of 2 g/dL (1.24 mmol/L) or more or leading to transfusion of two or more units of whole blood or red cells. 
2. Feasibility: Device success defined as the ability to use the Bashir™ Endovascular Catheter as described in this protocol.

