6.2.1 Primary Endpoints

1. Safety: Major bleeding, as defined by International Society of Thrombosis and Hemostasis (ISTH), within 72 hours of initiation of r-tPA administration. Bleeding criteria are as follows: Major Bleeding in Non-Surgical Patients.
 - a. Fatal bleeding; and/or
 - b. Symptomatic bleeding in a critical area or organ, such as intracranial, intraspinal, intraocular, retroperitoneal, intraarticular or pericardial, or intramuscular with compartment syndrome; and/or
 - c. Bleeding causing a fall in hemoglobin level of 2g/dL (1.24mmol/L) or more or leading to transfusion of two or more units of whole blood or red cells.²³
2. Feasibility: Device success defined as the ability to use the Bashir™ Endovascular Catheter as per this protocol.

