16.0 STATISTICAL CONSIDERATIONS

16.1 Sample Size Justification

The sample size selected (10) is considered to be a number sufficient to gather essential early information on the safety and performance of the device. The essential information is identified in the primary and secondary endpoints defined. The sample size will also assist in identifying additional meaningful data points, refine study endpoints, and improve study procedures before proceeding to a larger statistically powered pivotal trial.

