19.0 VERSION CONTROL

Add to table below for each protocol amendment

PROTOCOL THRO-CLIN-2018-01		
VERSION	SUMMARY OF THE CHANGE	RATIONALE
0.0	Original for FDA Review	N/A
1.0	Efficacy study stopping rule added	Response to FDA Clinical Hold Letter
2.0	Efficacy study stopping rule wording clarified; Core Lab Contact Updated; Supplier of CathFlo® Activase changed from Sponsor to Site; Typographical errors corrected	Respond to FDA request; make additional corrections
3.0	r-tPA Infusion calculation correction; elimination of “end diastolic” referenced with CTA; Modify anticoagulation protocol for patients on Lovenox	Additional corrections and clarifications
4.0	Change BMI exclusion to >45; clarify heparin infusion duration; specify use of 7Fr sheath of appropriate length; add instruction to maintain patency of BEC with infusion pump after r-tPA infusion; re-order procedure steps for heparin bolus after obtaining access; Change 24 and 48 hour assessments start point from “start of r-tPA administration” to “end of r-tPA infusion”	Additional corrections and clarifications
5.0	Remove heparin infusion following completion of r-tPA infusion; administer Lovenox for anti-coagulation at completion of r-tPA through the completion of the 48-hour CTA. Continue anti-coagulation according to standard of care after the CTA is complete.	Edit protocol with recommendations from the sponsor’s Scientific Advisory Board
6.0	Change time of commencing r-tPA infusion in the IR Suite / Cath Lab and specify the window of time permitted for Lovenox to be started and then administered every 12 hours.	Prevent blood from clotting in the infusion limbs of the basket. Window added for clarification.

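### In-use catheter failures that follow the start of treatment and cause no SAE are not clearly counted by any device stopping rule, so every subject could fail the primary feasibility endpoint without a mandatory device-related pause

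*Combined protocol and SAP*

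**What the plan says.** Section 18.4 has two device rules.

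- 18.4.1 begins "Should it be suspected that a device caused a serious adverse event". It then requires DSM adjudication, return of the device and a root cause analysis, and leaves it to the DSM whether the study stops, is suspended or continues.
- 18.4.2 opens with its scope, "There are device malfunctions, or non-conformances, that may impact the patient and prevent treatment with an investigational device", and then sets the trigger: "if there are device failures that prevent three (3) patients from being treated in this study, the study shall be paused for re-evaluation".

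The primary feasibility endpoint (Section 6.2.1, item 2) is "Device success defined as the ability to use the Bashir™ Endovascular Catheter as per this protocol". Section 18.0 names device success as one of the two things the study is to demonstrate, and lists bleeding, device use and early efficacy as the basis of the stopping criteria. No stopping rule mentions the device-success endpoint or sets a threshold for it.

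On size, the synopsis says "Up to ten (10) subjects will be enrolled and treated". Section 16.1 gives a judgement, not a calculation: "The sample size selected (10) is considered to be a number sufficient to gather essential early information".

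**The concern.** The trigger and the endpoint measure different things. The endpoint asks whether the catheter could be used as the protocol describes, from insertion to removal. The trigger asks whether the patient was kept from treatment. A catheter can fail the first test and pass the second.

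Most of the protocol-described use comes after r-tPA flow has begun, so this gap covers most of the time in which the device can fail. In a first-in-man study, a recurring in-use fault could be repeated in later subjects, each with a basket left in the pulmonary artery and perhaps an incomplete infusion. No device rule would clearly require a review, the return of the catheter or a root cause analysis.

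**Working it through.** **Step 1: where in-use failures fall.** Section 9.2 step 6 starts r-tPA flow before the catheter enters the sheath. These steps follow: basket expansion (9.2 step 9), pulse spray with collapse and re-expansion (9.3.1), about 8 hours of infusion (9.3.2 and 10.1), and collapse and removal under fluoroscopy (10.2). A failure at any of them comes after drug flow has started.

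**Step 2: each rule against a failure of this kind with no SAE.**

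| Rule | Trigger | Mandatory pause? | Reached? |
|---|---|---|---|
| 18.4.1 | Suspected device-caused SAE | No, DSM decides | No |
| 18.4.2 | Device failure prevents treatment of three patients | Yes | Not on the natural reading |
| 18.2 | Two patients with death or unprovoked intracranial hemorrhage | Yes | No |
| 18.3 | RV:LV reduction below 0.06 in all of the first three patients | Yes | Only through the CT result |
| 18.1.1, 18.1.3 | Judgement on safety or benefit-risk | No | Discretionary |

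If all ten subjects fail device success but none is kept from treatment, the 18.4.2 count is 0 of the 3 required. This needs no assumed failure rate.

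**Step 3: size of the gap.** The plan gives no failure rate and no operating characteristic for the rule, so there is no figure to reproduce. The rates below are assumptions. Let p be the per-subject rate of in-use device failure and s the share of those failures that count as preventing treatment. Subjects are independent and n = 10. The pause probability is P(X ≥ 3), with X ~ Bin(10, p) if every failure counts and X ~ Bin(10, p·s) under the current rule.

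Worked case, p = 0.30, every failure counted: 1 − (0.7^10 + 10·0.3·0.7^9 + 45·0.3²·0.7^8) = 1 − (0.0282 + 0.1211 + 0.2335) = 0.617.

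| p | All counted | Current, s = 0.5 | Current, s = 0.25 | Current, s = 0 |
|---|---|---|---|---|
| 10% | 0.07 | 0.01 | 0.002 | 0 |
| 20% | 0.32 | 0.07 | 0.01 | 0 |
| 30% | 0.62 | 0.18 | 0.03 | 0 |
| 50% | 0.95 | 0.47 | 0.12 | 0 |
| 100% | 1.00 | 0.95 | 0.47 | 0 |

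**Step 4: 18.3 as a backstop.** Let q be the chance that one patient's reduction is below 0.06. The rule fires with probability q³. Section 4.2 reports a reduction of 0.42 (± 0.36) in the earlier ultrasound-catheter study. Taking 0.36 as an SD and assuming normality, q = Φ((0.06 − 0.42)/0.36) = Φ(−1) = 0.16, so q³ = 0.004. If device failure raised q to 0.5 or 0.9, q³ would be 0.125 or 0.73. From the fourth patient on, 18.3 gives no protection.

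**The case against.** A reader might infer that in-use failures can never force a pause, or that the present chance of one is simply 0%. The documents do not support either statement.

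- **18.3 can fire.** If failures left all of the first three patients with almost no RV:LV response, a pause would be mandatory. This stands, but the trigger is an imaging result and it covers three patients only.
- ***Treated* is undefined.** The lead-in to 18.4.2 speaks of malfunctions that may affect the patient, and the protocol describes treatment as pulse sprays plus an infusion run to completion. A basket that will not open in the artery, or a line that blocks early, could be argued to prevent that treatment. This stands too: the 0 in Step 3 is one reading. A mandatory rule should not turn on which reading is taken.
- **There is other oversight.** Section 17.0 gives the DSM the feasibility data and provides for a charter, which is not in the documents and might hold device triggers. 18.1.1 and 18.1.3 allow a recommendation to terminate, or a pause. 18.4.1 needs only suspicion, and the SAE definition includes important medical events that may need intervention, so a basket that needs an intervention to retrieve it could qualify. All this lowers the risk, but nothing in the protocol makes a pause mandatory for repeated device failure without an SAE.
- **Version 6.0 reports no failure.** A reader might infer from Section 19.0 that catheters had already clotted in use. The stated rationale is preventive: "Prevent blood from clotting in the infusion limbs of the basket". It shows that the sponsor regards loss of patency as a hazard, and no more.
- **The study is small and descriptive.** Which faults should count, and how many, is for the sponsor and DSM to judge. That bears on the threshold, not on whether the rule should follow the endpoint.

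**Conclusion.** The concern holds in a limited form. 18.4.2 is keyed to prevented treatment, the primary feasibility endpoint is wider, and no device rule clearly counts an in-use failure without an SAE. Ten of ten endpoint failures without a mandatory device-related pause are possible on the natural reading of *treated*.

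The probabilities compare two counting definitions under assumed failure rates and do not estimate this catheter's performance. They also treat every counted failure as falling within ten subjects. If patients kept from treatment were replaced to reach ten treated, the current-rule figures would be somewhat higher. The result is a recommended improvement to a safety rule; it does not invalidate the study.

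**What to change.** In 18.4.2:

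1. Define *treated* and *device failure*.
2. Count toward the existing threshold of three, or another number set by the sponsor and DSM, any device-attributed failure of the primary feasibility endpoint, whether it prevents treatment or prevents protocol use to completion. Examples are loss of infusion patency, failure to expand, re-expand or collapse the basket, and unplanned early removal because of a device fault.
3. Require device return and root cause analysis for each such failure, as 18.4.1 already does for suspected device-caused SAEs.
4. Record device failures in the ICU and at removal on the CRF. Section 9.4 lists technical complications only for the procedure itself; the CRF is a separate document and should be checked.

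The cost is a short wording change and perhaps one added CRF item. The downside is that a pause for re-evaluation may come sooner, including for faults that prove minor. A pause under 18.4.2 is for re-evaluation and does not end the study.

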18.5 Study Safety Reporting Requirements

The following reporting requirements are the responsibility of the sponsor and are transferred to Eminence Clinical research, Inc. to meet these reporting obligations. For investigations of marketed drugs under an IND, such as in this study requiring the administration of FDA approved r-tPA, Eminence Clinical Research, Inc. shall submit IND safety reports for suspected adverse reactions that are observed in the clinical study at study sites (21 CFR 312.32).

[name]
Eminence Clinical Research, Inc.
Principal Regulatory Consultant
[contact]
[contact]

19.0 VERSION CONTROL

Add to table below for each protocol amendment

PROTOCOL THRO-CLIN-2018-01		
VERSION	SUMMARY OF THE CHANGE	RATIONALE
0.0	Original for FDA Review	N/A
1.0	Efficacy study stopping rule added	Response to FDA Clinical Hold Letter
2.0	Efficacy study stopping rule wording clarified; Core Lab Contact Updated; Supplier of CathFlo® Activase changed from Sponsor to Site; Typographical errors corrected	Respond to FDA request; make additional corrections
3.0	r-tPA Infusion calculation correction; elimination of “end diastolic” referenced with CTA; Modify anticoagulation protocol for patients on Lovenox	Additional corrections and clarifications
4.0	Change BMI exclusion to >45; clarify heparin infusion duration; specify use of 7Fr sheath of appropriate length; add instruction to maintain patency of BEC with infusion pump after r-tPA infusion; re-order procedure steps for heparin bolus after obtaining access; Change 24 and 48 hour assessments start point from “start of r-tPA administration” to “end of r-tPA infusion”	Additional corrections and clarifications
5.0	Remove heparin infusion following completion of r-tPA infusion; administer Lovenox for anti-coagulation at completion of r-tPA through the completion of the 48-hour CTA. Continue anti-coagulation according to standard of care after the CTA is complete.	Edit protocol with recommendations from the sponsor’s Scientific Advisory Board
6.0	Change time of commencing r-tPA infusion in the IR Suite / Cath Lab and specify the window of time permitted for Lovenox to be started and then administered every 12 hours.	Prevent blood from clotting in the infusion limbs of the basket. Window added for clarification.

21.0 APPENDICES

APPENDIX 21.1 REQUIRED STUDY PROCEDURES

Test	Pre-Procedure	Procedure	Post-Procedure	End of Infusion	24 Hrs Post-r-tPA Completion	48 Hrs Post-r-tPA Completion	72 Hrs Post- r-tPA Initiated	Before Discharge	30-day Follow-up
Visit Window	≤ 48 Hrs of procedure			+8 Hrs	± 8 Hrs	± 6 Hrs	-4 / +12 Hrs	-8 Hrs	± 7 Days
Informed Consent	X								
Demographics and Medical History	X								
Physical Examination	X			X	X			X	X
12 Lead ECG	X							X	
CBC, INR ¹	X		X ²		X				
aPTT	X ²		X	X					
Fibrinogen ³	X			X					
CMP	X								
BMP					X				
Cardiac Biomarkers: Troponin I, BNP	X				X				
Lower Extremity Venous DUS	X								
Contrast Enhanced CTA of the Chest	X						X		
RV/LV Diameter Ratio with each CTA	X						X		
Echocardiogram	X				X				
RV/LV Diameter Ratio with each Echocardiogram	X				X				
Eligibility Criteria	X	X							
Anticoagulation ³ (Heparin, Lovenox)	X	X	X	X	X	X			
IR / Cath Lab: Invasive Hemodynamic Data / ACT ⁴		X		X					
IR / Cath Lab: r-tPA Pulse Sprays Administration		X							
Bashir™ Endovascular Catheter(s) and r-tPA Use ⁵		X	X	X					
ICU: PAS / PAD / Mean PA q 30 Min via BEC			X	X					
ICU: Mixed venous SvO ₂ q2 Hours via BEC			X	X					
r-tPA Infusion		X	X						
Medications	X	X	X	X	X	X	X	X	X
AEs / SAEs		X	X	X	X	X	X	X	X
Contrast Enhanced CTs to Core Lab	X					X			
Echocardiograms to Core Lab	X				X				

¹INR is only required at baseline for patients on Coumadin (warfarin) and must be ≤ 1.5 prior to enrollment. If patient is eligible for the study, Coumadin will be discontinued temporarily for study purposes.

[figure not shown]
²Pre-procedure suggested aPTT 60-80s. Suggested aPTT during r-tPA administration is 40-60s. Check aPTT and CBC 4 hr (± 1 hr) after heparin is restarted in the IR suite/Cath lab (suggested range 60-80s).

[figure not shown]
³Unfractionated Heparin will be infused IV pre-procedure or Lovenox. Stop Heparin prior to start of procedure. Restart Heparin post procedure with r-tPA infusion. Fibrinogen to be drawn at time of BEC removal in IR suite/Cath lab. Heparin infusion will continue until the completion of the r-tPA infusion. Lovenox 1mg/kg Sub-Q will be started 45 minutes (± 15 minutes) from the completion of the r-tPA infusion and given q12hrs (± 30 min).

⁴Required: PAS, PAD, PA Mean, CO, CI, SpO₂, SvO₂ / ACT - in IR/Cath lab at baseline (print waveforms) and post-infusion in the IR suite/Cath Lab. Swan-Ganz or angled pigtail may be used. CO= Modified Fick calculation. ACT will be done to achieve (and document) an ACT ≥ 200 seconds.

⁵IV solution must be mixed according to protocol and infuse at the prescribed rate into target PA, or both PAs if bilateral PE. Infusion is to be administered at the rate prescribed in this protocol, which is a duration of approximately 8 hours. Once the r-tPA infusion is complete, heparinized saline must infuse TKO using the infusion pump until BEC removal.

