6.2.2 Secondary Endpoints

1. All-cause mortality at hospital discharge through 30-day follow-up.
2. SAEs through 30-day follow-up.
3. Anticipated (non-serious) adverse events (AEs) through 30-day follow-up.
4. Recurrent PE through 30-day follow-up.
5. Clinically Relevant Non-Major bleeding: Any sign or symptom of hemorrhage (e.g. more bleeding than would be expected for a clinical circumstance, including bleeding found by imaging alone) that does not fit the criteria for the ISTH definition of major bleeding but does meet at least one of the following criteria:
 - a) Requiring medical intervention by a healthcare professional.
 - b) Leading to hospitalization or increased level of care.
 - c) Prompting a face to face (i.e., not just a telephone or electronic communication) evaluation.
6. Technical procedural complications.
7. RV/LV end diastolic diameter ratio at 24 hours after completion of r-tPA infusion compared to baseline, by echocardiogram.

8. RV/LV diameter ratio at 48 hours after completion of r-tPA infusion, by contrast enhanced chest CTA compared to baseline.
9. Modified Miller Index at 48 hours post r-tPA infusion as compared to baseline by contrast enhanced chest CTA.
10. Systolic PA pressure measured at completion of infusion and compared to baseline.
11. Cardiac output (CO by modified Fick calculation) and cardiac index (CI) following completion of the r-tPA infusion compared to the baseline. Please refer to Terms and Definitions section for the modified Fick calculation to be done in the IR suite/Cath lab.

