10.4 Tests Required 48 Hours Following End of r-tPA Infusion

10.4.1 Imaging

1. **Contrast Enhanced CTA of the Chest** – A contrast enhanced chest CTA will be performed at 48 hours (± 6 hours) after completion of the r-tPA infusion. The contrast enhanced chest CTA is used to determine the post-procedure RV/LV diameter ratio and Modified Miller Index Score. Please note that subject must be on Lovenox 1mg/kg every 12 hours through the completion of the 48-hour CTA. *The CT will be sent to the core lab for analyses.*

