10.6 Tests Required 72 Hours (+12 hours) Following Start of r-tPA Administration

10.6.1 Assessments

1. **AE/SAEs** – Adverse events will be monitored and reported on the CRF post-procedure through discharge. *Bleeding complications will be assessed through 72 hours (-4 / +12 Hours) following initial administration of the first r-tPA dose that was administered in the IR suite/Cath lab.*

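### As extracted, Appendix 21.1 schedules the post-treatment chest CTA in the 72-hour column, whereas Section 10.4, endpoints 8 and 9 and rule 18.3 use a 48-hour scan; at the planned infusion length the two windows do not overlap

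*Combined protocol and SAP*

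**What the plan says.** Section 10.4.1 places the only post-treatment chest CTA at "48 hours (± 6 hours) after completion of the r-tPA infusion". Section 10.4.3 repeats that timing for the RV/LV ratio by CTA and has the core lab score the Modified Miller Index from the scan. In Section 6.2.2, item 8 is "RV/LV diameter ratio at 48 hours after completion of r-tPA infusion, by contrast enhanced chest CTA compared to baseline", and item 9 is the Modified Miller Index at the same time. The efficacy stopping rule in Section 18.3 refers to CT at 48 hours in the first three patients.

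Section 10.6 covers the 72-hour visit and asks for adverse events, bleeding and medications only. Its bleeding window is "72 hours (-4 / +12 Hours) following initial administration of the first r-tPA dose".

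Appendix 21.1 has nine visit columns. As extracted:

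- "Contrast Enhanced CTA of the Chest": marked pre-procedure and in the 72-hour column.
- "RV/LV Diameter Ratio with each CTA": marked pre-procedure and in the 72-hour column.
- "Contrast Enhanced CTs to Core Lab": marked pre-procedure and in the 48-hour column.

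**The concern.** The required-procedures table is an operative instruction that coordinators are likely to schedule from. If it sends the subject to CT in a different window from the one that defines the endpoints, scans may be taken at two different times across sites and pooled as one 48-hour value. The table also disagrees with itself: the scan is due at the core lab one visit column before the column in which it is taken.

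With up to ten subjects, each off-window scan is at least a tenth of the data for endpoints 8 and 9. Rule 18.3 pauses the study only when all three of the first three patients fall short of a 0.06 reduction, so a single scan can decide whether it triggers. That rule names no starting point for its 48 hours, so it depends on clear timing elsewhere. Section 14.1 allows deviations only to protect the patient, yet a site that follows either instruction deviates from the other.

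**Working it through.** **Inputs**

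- Section 9.3.2: unilateral infusion 750 cc at 95 cc/h; bilateral infusion 500 cc per catheter at 65 cc/h, both catheters at once.
- Section 4.3: 10 mg at 1.27 mg/h, stated as 7.87 hours. Sections 9.3.2 and 10.1 and the Appendix 21.1 footnotes say approximately 8 hours.
- Section 10.4.1: CTA at 48 ± 6 h after completion, that is 42 to 54 h.
- Section 10.6.1 and the Appendix 21.1 window row: 72 h, -4/+12 h, after initiation.

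**Step 1: reproduce the plan's infusion time.** Duration T = volume / rate.

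- Unilateral: 750 / 95 = 7.89 h (by dose, 10 / 1.27 = 7.87 h).
- Bilateral: 500 / 65 = 7.69 h.

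Both agree with the stated figure of approximately 8 hours.

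**Step 2: put both windows on the initiation clock.** The Section 10.4.1 window becomes T + 42 to T + 54.

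- Unilateral: 49.9 to 61.9 h.
- Bilateral: 49.7 to 61.7 h.
- T = 8 h: 50 to 62 h.
- Appendix 72-hour column: 72 - 4 = 68 h to 72 + 12 = 84 h.

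**Step 3: gap between the windows.** Gap = 68 - (T + 54) = 14 - T.

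| Time from first r-tPA to completion | Gap |
|---|---|
| 7.69 h | 6.3 h |
| 7.89 h | 6.1 h |
| 8 h | 6 h |
| 10 h | 4 h |
| 12 h | 2 h |
| 14 h | 0 h |

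The heading of Section 10.6 gives only +12 hours. If the lower limit were 72 h, the gap for the unilateral case would be 72 - 61.9 = 10.1 h.

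**Step 4: is this a column shift from the PDF reading?** Both CTA rows have the full nine visit cells, with the second mark in cell 7; the core-lab CT row has its second mark in cell 6. Other rows agree with the body text:

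- Echocardiogram and cardiac biomarkers: 24-hour column, as in Section 10.3.
- 12-lead ECG: pre-procedure and before discharge, as in Sections 7.1.3 and 10.7.1.
- Physical examination: pre-procedure, end of infusion, 24 hours, discharge and 30 days, as in Sections 7.1.3, 10.3.3, 10.7.1 and 11.1.
- Fibrinogen: pre-procedure and end of infusion, as in Sections 7.1.1 and 10.2.

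Without the two CTA marks, the 72-hour column holds only medications and adverse events, which is what Section 10.6 lists. A general shift is therefore unlikely. A local slip in two adjacent rows cannot be excluded from the extracted text.

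**The case against.** The strongest objection is that the evidence is the position of marks in a machine-read table. An extraction program can pad or shift a row, and correct neighbouring rows do not rule out a slip confined to two lines. This lowers the certainty and makes a check of the source table the first step. It does not remove the point, because the rows are complete and those around them align.

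The second objection is that the body text is explicit and unanimous. Endpoints 8 and 9 are clearly defined, no primary endpoint or sample size is touched, and the study is descriptive. That is correct. The risk lies in how sites carry out the schedule, not in how the endpoints are defined.

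A reader might infer more than the documents support:

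- *That a later scan overstates the 48-hour reduction.* No passage gives a rate of change of RV/LV ratio or clot burden between the two windows, so neither size nor direction can be stated.
- *That a later scan prolongs anticoagulation.* Section 10.5.2 allows any approved regimen once the scan is done, so anticoagulation does not simply end there, and the appendix's own anticoagulation marks stop in the 48-hour column. What can be said is that these passages must agree with whichever scan time applies.
- *That the gap is at least 6 h or as much as 34 h.* The first figure assumes that time from first r-tPA to completion equals pump time, although Sections 9.2 and 9.3.1 start the infusion before catheter insertion and pause it for the pulse sprays. The second, 84 - 49.7 = 34.3 h, is the distance between the outer edges of the two windows, not a gap.
- *That scans have already been mistimed.* The documents show no such scan.

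**Conclusion.** The point stands as an internal inconsistency, subject to a check of the source table. As extracted, Appendix 21.1 puts the post-treatment CTA and its RV/LV ratio at 68 to 84 h after first r-tPA. Sections 10.4.1 and 10.4.3, endpoints 8 and 9, rule 18.3 and the table's own core-lab row use the 48-hour scan, which is about 50 to 62 h after initiation. This rests on two assumptions: first r-tPA to completion takes the nominal 7.7 to 8 h, and rule 18.3 means the Section 10.4.1 scan, the only post-treatment CT the body text schedules. The gap is then about 6 h; it shrinks with delay but stays positive for any total under 14 h. Under planned treatment no single scan time satisfies both instructions. The consequence is off-window imaging for two secondary endpoints and the early efficacy rule; the effect on the measured ratio is unknown. No sample size, power or error rate changes.

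**What to change.** 1. Check the two CTA rows against the source table.
2. If the marks are as extracted, reconcile those rows with Section 10.4.1, endpoints 8 and 9, Section 18.3 and the core-lab row, so that one scan time with one anchor and window applies throughout. State the anchor in Section 18.3 as well.
3. Reconcile the enoxaparin text tied to the 48-hour CTA (synopsis, Sections 10.1, 10.4.1, 10.5.1 and 10.5.2) and the appendix's anticoagulation marks with that same scan time.
4. Notify the sites.
5. Report the actual hour of each CTA relative to r-tPA completion, and flag any outside the window in the summaries of endpoints 8 and 9 and in any application of rule 18.3.

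The cost is a table correction in an amendment, a site notice and one derived timing variable. No procedures are added.
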